6.2 Analysis and Presentation of the Primary Endpoint

The primary endpoint is detection of TB disease recurrence (relapse or reinfection), defined as TB diagnosed by confirmation of *Mtb* by culture of sputum, during the period starting 14 days after the 2nd vaccination (Day 70, Visit 6) and ending 12 months after the 2nd vaccination (Day 421, Visit 8) as detailed in Table 1 and Table 2.

The primary analysis set for efficacy will be the mITT analysis set (defined in Section 3). The primary efficacy endpoint will in addition be analysed using the ITT and PP analysis sets. The analysis specified for the ITT and PP are to be regarded as supportive evidence.

For a participant to meet the primary endpoint (TB recurrence), a confirmation of *Mtb* by at least one culture positive result of the two separate sputum samples collected is required. In addition, samples sent for culture without TB symptoms and with positive results are considered as having met the primary endpoint. The number (and percentage) of participants meeting the primary endpoint will be summarised by treatment group and trial site and also by treatment group and trial period.

Time to primary endpoint (TB recurrence) will be estimated using the Kaplan-Meier (KM) method and compared between treatment groups stratified by trial site. The stratified log-rank statistic will be used to test the null hypothesis of no difference in the rates of primary endpoint (TB recurrence) over the follow-up period in the H56:IC31 compared to the placebo group. The trial was designed for the primary endpoint to be evaluated using a one-side α -level of 10%, thus the lower one-sided p-value for the log-rank test will be presented. If the p-value for the log-rank test is below 0.10 then the primary objective of the trial is considered met. The Median time to TB and the p-value for a two-sided test will be presented as well.

Time to primary endpoint (TB recurrence) will be presented by treatment in cumulative plots, i.e., inverted KM estimates. One plot per trial site will be made. Time to censoring will be marked on the curves and number of participants at risk per month from 14 days post 2nd vaccination (or Day 70 for those who did not receive a second vaccination) will be presented. Month will be calculated as days divided by 30.25 and rounded to nearest integer.

Furthermore, time to primary endpoint (TB recurrence) will be presented by treatment in cumulative plots without stratification by trial site. Two plots will be presented, one plot including 80% confidence bands and one including 95% confidence bands.

The primary endpoint will additionally be analysed using a Cox proportional hazard regression model. The Cox proportional hazard model relies on the assumption of proportional hazards over time. The proportionality of the hazards by treatment will be evaluated using a graphical comparison of log-minus-log survival curves. If the proportional hazard assumption is found to be violated, the Cox regression model will be extended appropriately, e.g., by introducing a time-dependent variable or include trial sites as strata. The Cox proportional hazard model will include treatment and site as fixed effects. Treatment group inference will be evaluated using a two-sided likelihood ratio test. Vaccine efficacy (VE) will be calculated as 1 minus the hazard ratio for H56:IC31 versus placebo and presented together with both 80% and 95% profile confidence limits.

As a sensitivity analysis, the above will be repeated:

- Excluding participants who received 2nd vaccination outside the +/- 10 days visit window i.e., before day 46 or after day 66.
- Excluding positive results of samples sent for culture without TB symptoms or positive GenExpert.

The cumulative incidence of primary endpoint (TB recurrence) per 100 person-years with associated 95% confidence intervals during follow-up will be summarised by treatment group and by treatment group and trial site. Person-days of observation will be used to estimate the time at risk of primary endpoint (TB recurrence) and will be calculated based on participant's date of last contact with the

trial or date of primary endpoint (TB recurrence) - whichever is earlier - minus the date of the 2nd vaccination plus 14 days. Person-years of observation will be calculated as person-days of observation divided by 365.25. The incidence of primary endpoint (TB recurrence) will be calculated as the number of cases of primary endpoint (TB recurrences) diagnosed during trial follow-up, divided by the total person-years of observation.

Comparison of the incidence of primary endpoint (TB recurrence) between treatment groups will be performed using relative risk summaries and corresponding 95% confidence intervals.

Supportive robustness and consistency analysis will be performed using the PP and ITT analysis sets (defined in Section 3).

All information from the two separate sputum samples collected at screening (Visit 1 and 2), Visit 8, STB Visit, and ET Visit will be listed by treatment, participant and visit for the ITT analysis set.

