For the immunogenicity cohort at the [REDACTED] TZ sites only (= first 50 randomized participants at [REDACTED] and first 50 randomized participants at [REDACTED] = in total 100 participants), see Table 2-1, whole blood will be collected and stimulated for WB ICS on V3= Day 0 and V6= Day 70, see Table 3-2. For the remaining participants and sites, there will be no collection of whole blood for WB ICS.

The immunogenicity cohort at the [REDACTED], TZ sites also serves as control cohort, see Section 7.4.5 and Table 2-1. Therefore there will be collection on V8= Day 421, of PBMCs and plasma for ICS and IgG ELISA and whole blood for RNA analysis and blood subset counts. These samples will be control samples for the corresponding immunology samples taken from participants under diagnosis of recurrent TB during the study, see Table 3-2.

TB signs and symptoms training will take place at all visits and telephone calls (TCs) from V3= Day 0 and onwards, and TB symptom screening at all visits and TCs from V4= Day 14 and onwards. The TC1 to TC5 will take place on the following days: Day 154, 196, 280, 322 and 364. If there is suspicion of TB at any of these occasions, based on the TB symptoms screening, 2 separate sputum samples will be obtained, and the case verification procedure (see details below) for recurrent TB disease will be initiated at a Suspected TB (STB) visit.

[figure not shown]
Participants who are withdrawn from the study within 6 months after the last product administration, will be contacted at least 6 months after the last product administration for recording of SAEs and AEs of special interest.

Referral for diagnosis and management of recurrent TB is triggered by the investigator based on clinical suspicion of recurrent TB. Participants will not be withdrawn from the study based on this referral but will be withdrawn if *Mtb* positive by culture in the study or if the referral clinic diagnoses recurrent TB and starts TB treatment. The case verification procedure is initiated at a STB Visit.

Case verification procedure for recurrent TB disease:

- 2 separate sputum samples are obtained:
 - 1 sputum sample is tested by Xpert MTB/RIF Ultra
 - The same sputum sample and the second sputum sample are both sent for culture
 - The remainder of the 2 separate sputum samples is stored (frozen) as 2 separate samples for later analysis by WGS if recurrent TB is confirmed

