2.2.1 Sample Size Considerations

The sample size for this trial was based on the following assumptions:

1. Estimated TB Disease Recurrence rate in placebo group: 4%/year.
2. Follow-up period for each participant: 12 Months post Day 70.
3. Drop-out/loss to follow-up rate: 10%.
4. Vaccine Efficacy (VE): 60%.
5. Type I error rate: 20% (2-sided).

Sponsor: SSI & IAVI

Vaccine: H56:IC31

Trial: POR A-055

Date: 15 SEP 2023

Version: Final 2.0

Statistical Analysis Plan

Based on the above assumptions, a sample size of 900 participants (N=450 in each treatment arm) is expected to provide the 23 TB Disease Recurrence endpoints per active versus placebo comparison required to detect with 80% power a vaccine efficacy (VE) of 60%, assuming a 10% drop-out rate (i.e., 10% excluding participants who discontinue due to TB) and 12-month post Day 70 follow-up period for each participant.

3 Analysis Populations

The following 6 analysis sets are defined in the protocol and will be used in the analyses of the data:

- Safety analysis set: The safety analysis set will consist of all participants who received at least one dose of investigational product. Participants will be evaluated according to vaccination actually received. The safety analysis set will be used for evaluation of endpoints related to safety.
- Modified intention-to-treat (mITT) analysis set: The mITT will include all randomised participants except those with TB disease recurrence before Visit 6, Day 70 (or 14 days after the 2nd dose for those who received both vaccinations). Participants will be evaluated as randomised. The mITT is the primary analysis set for the primary and secondary efficacy endpoints.
- Second modified intention-to-treat (mITT2) analysis set: The mITT2 will include all randomised participants except those with TB disease recurrence prior to 30 days after the 1st dose. Participants will be evaluated as randomised. The mITT2 is the analysis set for the 3rd exploratory efficacy endpoint (section 6.5).

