6.1 Time-to-event analyses

Time-to-event analyses will have start- and end-timepoint depending on the endpoint and analysis set as described in Table 1 and Table 2 below:

Table 1: Start-timepoints in time-to-event analyses

Endpoints	Population	Start-timepoint (Day=0)
All	All	Excluded from analysis if withdrawal or event before the day of the start-timepoint.
Primary endpoint (TB recurrence)	PP	Date of 2 nd vaccination + 14 days
Primary endpoint (TB recurrence) Secondary endpoint (TB disease relapse) Secondary endpoint (TB disease reinfection)	mITT	1. If received 2 nd vaccination then date of 2 nd vaccination + 14 except if withdrawn before 2. If missed 2 nd vaccination and visit 6 is within ± 3 days visit window (Day 67 to 73) then visit 6 3. Else Day 70 except if withdrawn before
1 st exploratory endpoint (TB recurrence or new TB treatment) 2 nd exploratory endpoint (TB recurrence - Xpert MTB/RIF Ultra or culture of sputum)	ITT	Date of 1 st vaccination
3 rd exploratory endpoint (TB recurrence)	mITT2	Date of 1 st vaccination + 30 except if withdrawn before

If TB event is not within the period between the start-timepoint and end-timepoint, then the participant will be censored as described in Table 2. Events on the day of the start time-point are included in the analyses with a time-to-event duration of 1 day.

Table 2: End-timepoints in time-to-event analyses

Endpoint	Population	End-timepoint
All	All	Completing the trial, terminating early or lost-to-follow-up without events are censored at the day of the last visit. End-timepoint is always on the day or after the start-timepoint.
Primary endpoint (TB recurrence)	PP mITT ITT	Event: 1. Date of sputum collection for culture-confirmed TB disease Censored: Earliest date of the following: 1. Date of last visit or TC, regardless of whether two sputum samples were collected 2. Date of sputum collection resulting in positive Xpert MTB/RIF Ultra (if followed by new TB treatment) for culture negative participants 3. Date of onset of new TB treatment, in the absence of any prior culture-confirmed TB disease recurrence

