Number of recurrent cases, N(%)	xx (xx.x)	xx (xx.x)	
Person years of follow-up	xxxx	xxxx	
TB recurrence incidence rate* (95% CI)	x.x (x.x – x.x)	x.x (x.x – x.x)	x.x (x.x – x.x)
Site A1			
Number of participants contributing to analysis (N)	xx	xx	
Number of recurrent cases, N(%)	xx (xx.x)	xx (xx.x)	
Person years of follow-up	xxxx	xxxx	
TB recurrence incidence rate* (95% CI)	x.x (x.x – x.x)	x.x (x.x – x.x)	x.x (x.x – x.x)
Site A2			
...	

Page 1 of x

CI: Confidence intervals, TB: Tuberculosis

*Rate per 100 person-years of follow-up

Day 70 is interpreted as 2nd vaccination + 14 days.

Trial: <Trial id>

Program: <program_name>.sas - output: <output_name>.rtf - executed: DDMMMYYYY

Table 14.2.1.5: Analysis of TB recurrence from day 0 – culture of sputum – ITT set

<Layout similar to table 14.2.1.2>

Table 14.2.1.6: Supportive analysis of TB recurrence from day 0 – culture of sputum – ITT set

<Layout similar to table 14.2.1.3>

Table 14.2.1.7: Rate of TB recurrence from day 0 overall and by trial site– culture of sputum – ITT set

<Layout similar to table 14.2.1.4>

Table 14.2.1.8: Analysis of TB recurrence from day 70 – culture of sputum – PP set

<Layout similar to table 14.2.1.2>

Table 14.2.1.9: Supportive analysis of TB recurrence from day 70 – culture of sputum – PP set

<Layout similar to table 14.2.1.3>

Sponsor: SSI & IAVI Vaccine: H56:IC31 Trial: POR A-055	Document type: Table shells	Status: Final Version: 2.0 Date: 15 SEP 2023	
--	--------------------------------	--	--

Table 14.2.1.10: Rate of TB recurrence from day 70 overall and by trial site– culture of sputum – PP set

<Layout similar to table 14.2.1.4>

Table 14.2.1.11: TB recurrence during the trial by period – culture of sputum – ITT set

	H56:IC31 N (%)	Placebo N (%)
ITT set	xxx	xxx
TB recurrence		
Sputum samples sent for culture*	xx (xx.x)	xx (xx.x)
Recurrence	xx (xx.x)	xx (xx.x)
1 st vaccination to 30 days post 1 st vaccination	xx (xx.x)	xx (xx.x)
Relapse	xx (xx.x)	xx (xx.x)
Reinfection	xx (xx.x)	xx (xx.x)
Undetermined	xx (xx.x)	xx (xx.x)
31 days post 1 st vaccination. to before 2 nd vaccination**	xx (xx.x)	xx (xx.x)
Relapse	xx (xx.x)	xx (xx.x)
Reinfection	xx (xx.x)	xx (xx.x)
Undetermined	xx (xx.x)	xx (xx.x)
2 nd vaccination to 14 days post 2 nd vaccination	xx (xx.x)	xx (xx.x)
Relapse	xx (xx.x)	xx (xx.x)
Reinfection	xx (xx.x)	xx (xx.x)
Undetermined	xx (xx.x)	xx (xx.x)
15 days post 2 nd vaccination to EoT	xx (xx.x)	xx (xx.x)
Relapse	xx (xx.x)	xx (xx.x)
Reinfection	xx (xx.x)	xx (xx.x)

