<Layout similar to table 14.2.2.3>

Table 14.2.9.1: TB recurrence during the trial by period – culture of sputum – mITT2 set

<Layout similar to table 14.2.1.11>

Sponsor: SSI & IAVI Vaccine: H56:IC31 Trial: POR A-055	Document type: Table shells	Status: Final Version: 2.0 Date: 15 SEP 2023	
--	--------------------------------	--	--

Table 14.2.9.2: Analysis of TB recurrence from day 30 – culture of sputum – mITT2 set

<Layout similar to table 14.2.7.2>

Table 14.2.9.3: Sensitivity analysis of TB recurrence from day 30 – culture of sputum – mITT2 set

<Layout similar to table 14.2.7.3>

Table 14.2.9.4: Rate of TB recurrence from day 30 overall and by trial site – culture of sputum – mITT2 set

<Layout similar to table 14.2.2.3>

Table 14.3.1.1: Summary of adverse events – safety analysis set

	H56:IC31 N (%) E	Placebo N (%) E
Safety analysis set (N)	xxx	xxx
Any adverse event	xx (xx.x) xx	xx (xx.x) xx
Solicited AE	xx (xx.x) xx	xx (xx.x) xx
AESI	xx (xx.x) xx	xx (xx.x) xx
SAE	xx (xx.x) xx	xx (xx.x) xx
Fatal AE	xx (xx.x)	xx (xx.x)
Related AE	xx (xx.x) xx	xx (xx.x) xx
Related SAE	xx (xx.x) xx	xx (xx.x) xx
SUSAR	xx (xx.x) xx	xx (xx.x) xx
AE leading to discontinuation of IMP	xx (xx.x) xx	xx (xx.x) xx
AE leading to discontinuation of trial	xx (xx.x) xx	xx (xx.x) xx
Intensity		
Severe	xx (xx.x) xx	xx (xx.x) xx
Moderate	xx (xx.x) xx	xx (xx.x) xx
Mild	xx (xx.x) xx	xx (xx.x) xx
Outcome		
Fatal	xx (xx.x) xx	xx (xx.x) xx
Not yet recovered	xx (xx.x) xx	xx (xx.x) xx
Recovered with sequelae	xx (xx.x) xx	xx (xx.x) xx
Recovered without sequelae	xx (xx.x) xx	xx (xx.x) xx
Unknown	xx (xx.x) xx	xx (xx.x) xx

Page 1 of x

N: Number of participants, %: Percentage of participants, E: Number of events.

Only treatment emergent AEs are presented, Solicited AEs: Events occurring within 7 days after a vaccination and of the following types: the injection site reactions redness, swelling, and tenderness/pain, and the systemic adverse events fever, arthralgia, myalgia, fatigue, headache, rash, chills, and nausea. AESI: Adverse event of special interest,

SAE: Serious adverse event, SUSAR: Suspected unexpected serious adverse reaction

Trial: <Trial id>

Program: <program_name>.sas – output: <output_name>.rtf - executed: DDMMYYYY

Table 14.3.1.2: Adverse events by SOC and preferred term – safety analysis set

	H56:IC31 N (%) E	Placebo N (%) E
Safety analysis set (N)	xxx	xxx
Any adverse event	xx (xx.x) xx	xx (xx.x) xx
<System organ class 1>	xx (xx.x) xx	xx (xx.x) xx

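### The person-time rule in SAP 6.2 starts at dose 2 + 14 days, so it does not fit the ITT rate from Day 0 and gives one-dose mITT participants no start date

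*SAP*

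**What the plan says.** **The rule.** SAP 6.2 gives the only explicit person-time formula. The end is last contact or recurrence, "whichever is earlier - minus the date of the 2nd vaccination plus 14 days". Protocol 7.3.1 has the same start. The SAP wording could also be read as adding 14 days to the difference; the protocol wording makes clear that the start is the day 14 days after dose 2. The paragraph does not refer to Tables 1 and 2 and has no branch for a missed second dose.

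**Time-to-event dates.** SAP 6.1 sets start dates in Table 1 and end dates in Table 2. In the mITT, a participant who missed dose 2 starts at Visit 6 if that visit was in window: "Else Day 70 except if withdrawn before". The number-at-risk counts in 6.2 also use Day 70 for such participants. For the primary endpoint, Table 2 censors at new TB treatment, and at a positive Xpert followed by treatment in culture-negative participants. Section 6.1 caps a late last visit at Day 428.

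**Rate tables.** SAP Section 9 moves the ITT analysis of the primary endpoint to a Day 0 start, and the shells include "Table 14.2.1.7: Rate of TB recurrence from day 0 overall and by trial site". For the mITT2 set they include "Table 14.2.9.4: Rate of TB recurrence from day 30 overall and by trial site". SAP 6.3 and 6.5 ask for rates per 100 person-years without defining person-time. Protocol 7.3.2 says that the secondary and exploratory endpoints use the methods of the primary.

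**The concern.** One rule, tied to dose 2, stands behind rates with different origins. In the ITT from Day 0, cases enter the numerator from the first vaccination while time enters the denominator only from about Day 70. In the mITT, participants without dose 2 have no start date under the rule, though the log-rank and Cox analyses of the same set give them one. The end date also differs, because the rule ignores the Table 2 censoring events and the Day 428 cap.

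The rates and relative risks would then rest on different time at risk from the log-rank and Cox results beside them. Absolute recurrence by arm and site is a planned output of a trial that protocol 1.6 describes as informing Go/No Go decisions, and it is a figure from which a later trial would be planned. As written, a programmer must either follow a rule that yields negative time or make an undocumented choice.

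**Working it through.** **1. The plan's own figure.** The documents state no person-time or incidence result, so the only design figure to reproduce is the 23 events in SAP 2.2.1. Inputs: "Estimated TB Disease Recurrence rate in placebo group: 4%/year", efficacy 60% (hazard ratio 0.40), two-sided alpha 20%, power 80%, 450 per arm, 10% drop-out.

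- Schoenfeld: 4 × (1.2816 + 0.8416)² / (ln 0.40)² = 21.48, so 22 events.
- Freedman: (1.2816 + 0.8416)² × (1.4/0.6)² = 24.54, so 25 events.
- Expected: 450 × 0.9 × (0.04 + 0.016) = 22.68, so 23 events.

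The 23 reproduces and is not in question. The design rates are used below.

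**2. ITT rate from Day 0 (Table 14.2.1.7).** Assumptions: constant hazard of 4% per year on placebo and 1.6% on vaccine, 450 per arm, dose 2 on Day 56, end on Day 421, no drop-out. Time at risk runs 421 days from Day 0; the 6.2 rule counts 421 − 70 = 351. It removes 450 × 70/365.25 = 86.2 person-years (PY) per arm.

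| Arm | Events | PY from Day 0 | Rate per 100 PY | PY by 6.2 rule | Rate per 100 PY |
|---|---|---|---|---|---|
| Placebo | 20.28 | 506.9 | 4.00 | 420.7 | 4.82 |
| H56:IC31 | 8.22 | 513.9 | 1.60 | 427.7 | 1.92 |

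The simple ratio is 421/351 = 1.199. With Day 70 as the nominal start, a Day 40 recurrence contributes 40 − 70 = −30 days. About 3.4 placebo and 1.4 vaccine cases per 450 would fall before Day 70. Setting their time to zero instead gives the same rates, 4.82 and 1.92. The rate ratio is unchanged: 1.92/4.82 = 0.40, against 1.60/4.00 = 0.40.

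**3. mITT rate from Day 70.** For two-dose participants the start agrees with Table 1. For one-dose participants the rule gives no value. Their share is not in the documents, and the SAP does not say whether their cases would still be counted. If they were counted while the time was lost, a share p would multiply the rate by 1/(1 − p): 1.010, 1.053 and 1.111 for assumed shares of 1%, 5% and 10%. If both were left out, this inflation would not arise.

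**4. Day 30 rate (Table 14.2.9.4), if the 6.2 rule is carried over.** Time at risk is 421 − 30 = 391 days against 351 counted, a ratio of 1.114. The placebo rate becomes 18.86/422.3 = 4.47 instead of 18.86/471.6 = 4.00 per 100 PY. The vaccine rate becomes 7.64/428.3 = 1.78 instead of 7.64/477.6 = 1.60.

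**5. Can Tables 1 and 2 simply be used instead?** Not as they stand.

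- Table 1 has no ITT row for the primary, relapse or reinfection endpoints, and no mITT row for exploratory endpoints 1 and 2.
- Table 2 censors the third exploratory endpoint at dose 2 + 14, while 6.5.3 counts later events. Used as person-time, with cases through Day 421 still counted, this gives about 33.0 and 14.5 per 100 PY instead of 4.0 and 1.6.
- The + 1 day convention is negligible: 352/351 = 1.003.

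**The case against.** The strongest reply is that the intention is clear. Section 9 and the title of Table 14.2.1.7 say that the analysis starts at Day 0. Section 6.2 opens by defining the endpoint through Tables 1 and 2, and these give one-dose participants a start. A careful programmer would not accept negative time. This holds for the intention. But the only stated formula says otherwise, and Table 1 has no ITT row for the primary endpoint to fall back on.

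Four stronger readings are tempting, and the documents do not support them:

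- *One-dose participants inflate the mITT rate by a known amount.* Neither their share nor a rule that keeps their cases while dropping their time is stated. The rate shell has a separate row for participants contributing to the analysis, so both could be left out.
- *Every Day 0 and Day 30 table carries a wrong formula.* The 6.2 rule is written for the primary endpoint. For Tables 14.2.2.6, 14.2.3.4, 14.2.7.7, 14.2.8.7 and 14.2.9.4 person-time is undefined, and wrong only if 6.2 is carried over.
- *Time after withdrawal will be counted.* Participants withdrawn within 6 months of their last dose "will be contacted at least 6 months after the last product administration for recording of SAEs and AEs of special interest". Whether that call is a last contact for efficacy is inference; Table 2 uses the last visit or telephone call. Participants treated by the referral clinic are also withdrawn, so time in the study after new treatment should be short.
- *The primary result is at risk.* The log-rank test, the Cox efficacy estimate and the success criterion do not use this formula.

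**Conclusion.** The point holds for two outputs of the primary endpoint. For the ITT rate from Day 0 the stated rule is wrong: about 20% too high in each arm (4.82 against 4.00 per 100 PY on placebo), assuming a constant hazard, dose 2 on Day 56 and no drop-out. For the mITT rate the rule gives one-dose participants no start although the SAP supplies one elsewhere; the size of any effect cannot be fixed from the documents. The omission of the Table 2 censoring events and the Day 428 cap is a real mismatch of unknown, probably small, size. For the Day 30 table and the other Day 0 tables the fault is a missing definition, with about 11% overstatement at Day 30 if the 6.2 rule is carried over.

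The consequence is confined to descriptive absolute rates. The rate ratio barely moves if the arms are balanced in second-dose receipt and follow-up. The plan should be corrected, but the primary inference does not depend on it.

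**What to change.** In SAP 6.2, replace the person-time sentence with one rule for every endpoint and analysis set: person-days equal the Table 2 end-timepoint minus the Table 1 start-timepoint, plus 1. The rates then use the same time at risk as the log-rank and Cox analyses, and the ambiguous placing of the 14 days disappears. Two corrections must come first:

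1. Add the missing Table 1 rows: ITT from first vaccination for the primary, relapse and reinfection endpoints; mITT for exploratory endpoints 1 and 2, with the same start as the primary.
2. In Table 2, remove the censoring item at dose 2 + 14 for the third exploratory endpoint, so that the row agrees with 6.5.3.

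Sections 6.3 and 6.5 should refer to the same rule. The cost is one SAP sentence, a few table rows and reuse of derived variables; no new data are needed.
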